#### 7.3.3.1 Adverse events

As defined in section 8.2, an AE is any unfavorable medical occurrence in a subject to whom an PI is administered, regardless of the causal attribution.

The management of AEs will be carried out according to what is described in the Adverse Events section.

The IP will register in the corresponding section of the FERC the AE that the study subjects present in addition to referring it in the clinical file.

For an adequate evaluation of the AE, in addition to the directed questioning, it is necessary to carry out at each visit the Ophthalmological Ophthalmological Evaluation of the eyelids and attachments; anterior segment and posterior segment that is performed in a routine ophthalmological examination, whose procedures are not specifically included in the study variables. The posterior pole evaluation can be with direct or indirect ophthalmoscopy, with or without pharmacological mydriasis, at the discretion of the PI. An evaluation of the fundus will be carried out in search of abnormalities that alter the result of the study. The IOP will be measured in this evaluation, with the instrument of choice of the PI, it should be measured after the evaluation of the stains. The result of the assessment will be recorded in the clinical file. In the FERC, only the findings that are considered by the IP will be reported as EA.

Expected AEs for the use of IPs are: blurred vision, burning, eye irritation, foreign body sensation and sticky eyelash sensation. They are expected to be transient, lasting no more than 30 seconds after PI instillation, and to be of mild intensity..

#### 7.3.3.2 ICO score

The ICO is a questionnaire designed to measure the irritation of the ocular surface with Rasch analysis to produce estimates on a linear interval scale (scores: 0-100). Similar to the index for ocular surface diseases, the ocular comfort index (ICO) assesses symptoms. The ICO contains items that focus on discomfort associated with ocular surface disturbances. Each of these questions has two parts, which separately inquire about the frequency and severity of symptoms. [40]

The evaluator will deliver the questionnaire to the subject and will allow him to answer it calmly without any pressure and / or coercion, he will only assist him if he has difficulty understanding any of the questions.

Management as AE: The ICO assesses symptoms, which may or may not be related to an AE. The score obtained from the ICO alone should not be considered an EA.

#### 7.3.3.3 Best Corrected Visual Acuity

Visual acuity (VA) is a test of visual function. Spatial AV is the ability to distinguish separate elements of an object and identify them as a whole. It is quantified as the minimum angle of separation (located at the nodal point of the eye) between two objects that allows them to be perceived as separate objects.

Snellen's notation is described as the distance at which the test is performed, divided by the distance at which the letter is vertically equal to 5 arc minutes. Thus, at 6 meters a letter 6/6 (20/20) is equivalent to 5 arc minutes, a letter 6/12 (20/40) is equivalent to 10 minutes, and a letter 6/60 (20/200) is equivalent to 50 minutes. The Snellen fraction can also be expressed as a decimal (that is, 20/20 = 1 and 20/40 = 0.5). [41]

VA will be evaluated baseline, without refractive correction with the Snellen chart. Which will be located in a place with adequate natural or artificial lighting and at a distance of 3m from the subject to be evaluated. The visual acuity of each eye will be taken, starting with the right eye (OD) asking the subject to keep both eyes open and using an occluder to cover the left eye (OS); The subject will read aloud the lines that the evaluator indicates, the line of smallest letters that can be seen will be noted by the evaluator in fraction as the VA of OD in the clinical record. The OS is proceeded with the same method.

Subsequently, the subject's objective and subjective refractive correction will be carried out. The result of the subjective refraction will be reported as BCVA, it will be noted in fraction in the clinical record and in the FERC, also in the FERC it will be noted in decimal. By definition, BCVA cannot be lower than VA.

Handling as EA: a decrease of more than 2 lines in the Snellen chart should be reported and handled as EA.

#### 7.3.3.4 Corneal and conjunctival fluorescein staining

A drop of topical anesthetic will be instilled in the conjunctival cul-de-sac, then a second drop will be applied to the tip of the fluorescein strip allowing it to settle on the strip for 5 seconds to elute the dye, shaking off the excess at the end. A small contact of the strip with the conjunctiva is made in the temporal cul-de-sac, while the patient looks up, without damaging the conjunctiva. It will be graded according to the Oxford scale. [42]

The IP will record in the file and the FERC the grade awarded for fluorescein staining of OD and OS respectively.

Management as AE: corneal stains that are equal to or greater than grade III will be considered as AE.

#### 7.3.3.5 Conjunctival staining with lysamine green

After the fluorescein check, a drop of saline will be applied to the tip of the lysamine green strip, allowing it to settle on the strip for 5 seconds to elute the dye. A drop of the strip is instilled into the temporal cul-de-sac, while the patient looks up, without damaging the conjunctiva. The patient may be asked to blink repeatedly to avoid accumulation in the conjunctival folds. The examination should be done 1 to 4 minutes after instillation through a neutral density filter or with the filter free of red. It will be graded according to the Oxford scale. [42]

The IP will record in the file and the FERC the grade awarded for fluorescein staining of OD and OS respectively.

Management as AE: corneal stains that are equal to or greater than grade III will be considered as AE.

#### 7.3.3.6 Conjunctival hiperemia

Conjunctival hyperemia is defined as the simplest reaction of the conjunctiva to a stimulus, a red appearance is seen secondary to the vasodilation of the conjunctiva vessels of variable intensity. You will graduate using the Efron scale. [43] See annex.

Management as AE: conjunctival hyperemias classified as grade 3 or higher will be considered as AE..

#### 7.3.3.7 Chemosis

It is defined as conjunctival edema, the result of an inflammatory reaction. It is qualified as present or absent. The evaluator will use a narrow beam of light at 60 ° and will measure if the conjunctiva separates from the sclera by  $\geq 1/3$  of the total lid opening or if it exceeds the gray line. [44]

#### Handling as EA: your presence will be considered as an EA.

#### 7.4 Program of visits and study activities

#### 7.4.1 Description of activities per visit

The procedures are listed in the order that they are suggested to be performed, trying to maintain the coherence of the evaluations and, as far as possible, from the least invasive to the most invasive.

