#### 7.4.1.1 Basal visit

- -FCI Signature: refers to the signature of the written informed consent document. Without obtaining informed consent, it is not possible to perform any of the study procedures
- -Clinical history: refers to the technical, clinical and legal document in which the subject's health conditions, medical acts and other procedures performed on the subject are chronologically recorded. It includes anthropometric measurements, anamnesis, comprehensive ophthalmological examination that allows discerning the eligibility of the patient, that is, evaluation of both eyes of ocular attachments, slit lamp examination of the ocular surface and anterior segment, and funduscopy. If the subject is taken from the established population base of the study center, the existing clinical history may be used, only an update being required.
- -Evaluation of concomitant medications: refers to the questioning by the PI of the subject, inquiring about the use of medications.
- Pregnancy test in urine: It refers to the realization of a rapid pregnancy test in all women of childbearing age who wish to enter the study. By childbearing age we understand women who have had their menarche and have not had their menopause. Menopause is defined as 12 months from the last menstruation in women over 40 years of age, or who have undergone a bilateral hysterectomy or oophorectomy. Women of childbearing potential with contraceptive methods including bilateral tubal obstruction should undergo a pregnancy test. This test will be performed by the IP or the designated team person in accordance with the instructions of the device provided by the sponsor
- -Vital signs: refers to the taking of heart rate, respiratory rate, systemic blood pressure and temperature. This information must be contained in the patient's medical record and the progress notes of the patient's clinical record.
- -MAVC: See 7.4.3.2
- -ICO: See 7.4.3.2
- Ocular surface stains: See 7.4.3.4 and 7.4.3.5
- Ophthalmological evaluation: See 7.4.3.1
- -Eligibility criteria: refers to the review by the PI, where it verifies that the subject can be included in the study by meeting the inclusion criteria and not meeting the exclusion criteria. See 5.1

- -Assignment of PI: It refers to determining the intervention that the patient will follow during the study. It will be carried out according to section 7.3. This assignment will be made at the baseline visit (day 1).

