#### 7.4.1.2 Final Visit

- Evaluation of concomitant medications: See further 7.5.1.1
- -Pregnancy test in urine: See above 7.5.1.1
- -Vital signs: See above 7.5.1.1
- -MAVC: See 7.4.3.2
- Ocular surface stains: See 7.4.3.4 and 7.4.3.5
- -Integral ophthalmological evaluation: Ver7.4.3.1
- -Evaluation of EA: See 7.4.3.1
- -ICO: See 7.4.3.2
- -Evaluation of the Subject's Diary: See 7.5.1.1
- Evaluation of adherence: See 7.5.1.1
- Return of PI and subject's diary: refers to the return by the subject, of the PI and the subject's diary to the research center.

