#### 10.1.2 Interpretation of data

The Kolmogorov-Smirnov tests will be carried out to know if the distribution presents normality in the results obtained in each study group. [fifty]

The results of the continuous quantitative variables will be presented in measures of central tendency: mean, standard deviation and ranges.

The statistical analysis of the continuous quantitative variables to find significant differences (p < 0.05) will be as follows:

- Intra-group analysis: they will be determined using the Wilcoxon rank test for quantitative variables. [51]
- •
- Between-group analysis: The differences between the groups will be analyzed using the Mann-Whitney U test.

The level of difference to consider significance will be an alpha ( $\alpha$ ) of 0.05 or less.

The result of the nominal and ordinal qualitative variables will be presented in frequencies, proportions and percentages.

The statistical analysis to identify significant differences of the qualitative variables will be carried out by creating 2x2 contingency tables and will be carried out as follows:

- Intragroup difference: McNemar test. [52] Which is applied to 2 × 2 contingency tables with a dichotomous trait, with pairs of matched subjects, to determine if the marginal frequencies of row and column are equal (marginal homogeneity).
- Difference between groups: Pearson's Chi-square test (X2) or Fisher's exact test in expected values less than 5.

The level of difference to consider significance will be an alpha ( $\alpha$ ) of 0.05 or less.

For the reporting of adverse events, all the eyes of those participants who were randomly assigned to an intervention group after the baseline visit will be considered. The results will be expressed in number of subjects.

The final report of the results will be shown in tables or graphs, as appropriate.

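### The comfort questionnaire (ICO), a primary outcome, is listed before the anaesthetic and dyes at baseline but after them at the final visit, so its measurement conditions may differ between visits

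*Combined protocol and SAP*

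**What the plan says.** Section 7.4.1 states that "The procedures are listed in the order that they are suggested to be performed", aiming as far as possible to go "from the least invasive to the most invasive". The order of each visit list is therefore an instruction, though a soft one.

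- **Baseline visit (7.4.1.1).** Visual acuity is followed by "ICO: See 7.4.3.2", then the ocular surface stains, then the ophthalmological evaluation.
- **Final visit (7.4.1.2).** Visual acuity is followed by "Ocular surface stains: See 7.4.3.4 and 7.4.3.5", then "Integral ophthalmological evaluation", then the adverse event evaluation, and only then ICO.

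The staining procedure is set out in 7.3.3.4 and 7.3.3.5. It starts with "A drop of topical anesthetic will be instilled in the conjunctival cul-de-sac" and a fluorescein strip touched to the conjunctiva. The second dye comes next: "After the fluorescein check, a drop of saline will be applied to the tip of the lysamine green strip". Section 7.3.3.1 places the IOP measurement in the ophthalmological evaluation, after the stains, and leaves the instrument and any pharmacological dilation to the investigator.

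ICO at day 8 is one of two primary outcomes (7.3.1) and the only measure named for the tolerability objective (2.3.2). Section 7.3.3.2 describes how the questionnaire is handed over but gives no timing relative to drops or dyes. For within-group change, 10.1.2 says differences in quantitative variables "they will be determined using the Wilcoxon rank test for quantitative variables"; between groups it uses the Mann-Whitney test.

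**The concern.** The questionnaire touches nothing, so under the section's own ordering principle it belongs before the drops and dyes, where the baseline list puts it. The final-visit list reverses this. The ICO items (Annex 15.1) cover dry, gritty, stinging, tired, sore and itchy eyes. Anaesthetic can suppress such sensations, and dyes and examination can provoke them.

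Two analyses are affected in different ways. In the within-arm comparison of baseline with day 8, any effect of the changed order cannot be separated from change on treatment. In the between-arm comparison at day 8, procedure effects that differ from subject to subject add noise. Noise is not neutral here: section 10.1.5 judges the product by the absence of clinical and statistical differences from the comparator on all primary outcomes, so lost precision makes that finding easier to reach.

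**Working it through.** The documents give no figure to reproduce on this point. The check sets the two lists side by side, then asks which analyses a change of order can reach.

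**1. Order of the shared ocular assessments**

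| Position | Baseline (7.4.1.1) | Final visit (7.4.1.2) |
|---|---|---|
| 1 | Visual acuity | Visual acuity |
| 2 | **ICO** | Stains (anaesthetic, fluorescein, lissamine green) |
| 3 | Stains | Ophthalmological evaluation, with IOP |
| 4 | Ophthalmological evaluation | **ICO**, after the AE evaluation |

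ICO is second of four at baseline and last of four at the final visit.

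**2. Does other text override the lists?** Section 7.3.3.2 sets no timing. The schedule table in 1.2 has the ICO row below the staining row for both visits, but it makes no statement about order, whereas 7.4.1 does. Nothing resolves the difference.

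**3. Which analyses are affected?** Write the day-8 score as the score under baseline conditions plus a procedure effect, e = c + v, where c is common to all subjects and v varies between them.

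- *Within arm.* The paired change contains c directly. With no product effect, the Wilcoxon test is then testing c.
- *Between arms.* Adding the same c to every subject leaves all ranks unchanged, so the Mann-Whitney result does not move. Only v matters. If v is independent of the score and adds a fraction r to its variance, a true standardised difference d becomes d / √(1 + r).

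**4. Illustrations under assumed effects** (simulation, 4,000 runs, carried out twice; ranges show both results). The documents give no ICO standard deviation, target difference or procedure effect, so every c, r and d below is an assumption.

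Within arm, n = 17, no product effect, nominal level 5%:

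| Assumed c (SD of the change) | Rejection rate |
|---|---|
| 0.25 | about 14–15% |
| 0.5 | about 45–46% |

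Between arms, 17 per arm, assumed true d = 1.0:

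| Assumed r | Diluted d | Power |
|---|---|---|
| 0 | 1.0 | about 79% |
| 0.25 | 1/√1.25 = 0.894 | about 69–70% |
| 0.50 | 1/√1.50 = 0.816 | about 60–62% |
| 1.00 | 1/√2.00 = 0.707 | about 49–50% |

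These tables show what such effects would do, not that they exist.

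**The case against.** The case against giving this much weight is substantial, and most of it stands.

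- **The order is only suggested.** Nothing obliges the site to give ICO after the drops. This stands: a late day-8 ICO is where the list leads, not a requirement. But a loose order also lets timing vary from subject to subject, which is a reason to fix this one step.
- **The items ask about the past week, and usual intensity.** They do not ask how the eyes feel now. This stands as a reason to expect a smaller effect. It does not make conditions at the two visits the same.
- **Baseline is not free of examination.** The clinical history in 7.4.1.1 comes before ICO and includes slit-lamp examination and funduscopy, unless an existing history is only updated. Contact tonometry and dilation at the final visit are discretionary. This stands: the firm contrast is the anaesthetic and the two dyes, followed by an IOP measurement by an unspecified method.
- **The within-arm test is supporting.** It does not enter the rule in 10.1.5, and an uncontrolled before-after change cannot isolate a product effect even with a perfect order. This stands, and it limits what is at stake.
- **The rule that treats no difference as success is a separate matter.** It explains why noise is unwelcome; it does not make the order problem larger.

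A reader might go further and infer that the day-8 comparison between products is biased. The documents do not support that: both randomised arms have the same final-visit list, so a common shift cancels. Nor do they support saying that the day-8 score is certainly taken from anaesthetised and stained eyes.

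**Conclusion.** The inconsistency is real and can be read directly from 7.4.1.1 and 7.4.1.2: ICO moves from before the stains to after them, against the section's own principle. If the lists are followed, the within-arm baseline-to-day-8 ICO comparison is confounded with the change of order. The decisive between-arm day-8 comparison stays unbiased and loses precision only if reactions to the procedures differ between subjects.

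Confidence is high on the order difference and low on any material effect on the primary comparison. The direction is also open, since anaesthetic may lower scores while dyes and examination may raise them. The simulated rates rest entirely on assumed shifts, variances and a 1.0 SD true difference, and should not be read as estimates for this trial. The change is worth making because it costs almost nothing and gives a primary outcome the same conditions at both visits.

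**What to change.** In 7.4.1.2, move ICO to the place it has at baseline: after visual acuity and before the stains. In both visit lists, state as a requirement that ICO is completed before that visit's anaesthetic, dyes, IOP measurement and any mydriatic. A matching sentence in 7.3.3.2 would settle the timing where the questionnaire is defined.

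This is a free improvement. One line moves and one sentence is added, with no new procedure, visit time or subjects, and no change to clinical management. If the protocol is already approved, the amendment route in 11.2 applies (sponsor and/or investigator approval, committee review and regulatory authorisation), and the change can go in with any other amendment.

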#### 7.4.1.1 Basal visit

- -FCI Signature: refers to the signature of the written informed consent document. Without obtaining informed consent, it is not possible to perform any of the study procedures
- -Clinical history: refers to the technical, clinical and legal document in which the subject's health conditions, medical acts and other procedures performed on the subject are chronologically recorded. It includes anthropometric measurements, anamnesis, comprehensive ophthalmological examination that allows discerning the eligibility of the patient, that is, evaluation of both eyes of ocular attachments, slit lamp examination of the ocular surface and anterior segment, and funduscopy. If the subject is taken from the established population base of the study center, the existing clinical history may be used, only an update being required.
- -Evaluation of concomitant medications: refers to the questioning by the PI of the subject, inquiring about the use of medications.
- Pregnancy test in urine: It refers to the realization of a rapid pregnancy test in all women of childbearing age who wish to enter the study. By childbearing age we understand women who have had their menarche and have not had their menopause. Menopause is defined as 12 months from the last menstruation in women over 40 years of age, or who have undergone a bilateral hysterectomy or oophorectomy. Women of childbearing potential with contraceptive methods including bilateral tubal obstruction should undergo a pregnancy test. This test will be performed by the IP or the designated team person in accordance with the instructions of the device provided by the sponsor
- -Vital signs: refers to the taking of heart rate, respiratory rate, systemic blood pressure and temperature. This information must be contained in the patient's medical record and the progress notes of the patient's clinical record.
- -MAVC: See 7.4.3.2
- -ICO: See 7.4.3.2
- Ocular surface stains: See 7.4.3.4 and 7.4.3.5
- Ophthalmological evaluation: See 7.4.3.1
- -Eligibility criteria: refers to the review by the PI, where it verifies that the subject can be included in the study by meeting the inclusion criteria and not meeting the exclusion criteria. See 5.1

- -Assignment of PI: It refers to determining the intervention that the patient will follow during the study. It will be carried out according to section 7.3. This assignment will be made at the baseline visit (day 1).
- -Delivery of the PI and start of intervention: It refers to the delivery of the PI to the study patient, by the research center. See
- -Evaluation of EA: See 7.4.3.1
- -Delivery of patient material and filling instructions: It refers to the delivery by the IP to the subject of the subject's diary, identification card and calendar, improving adherence. The assigned personnel will carry out a previous training to the subject, on the filling of the diary.

#### 7.4.1.2 Final Visit

- Evaluation of concomitant medications: See further 7.5.1.1
- -Pregnancy test in urine: See above 7.5.1.1
- -Vital signs: See above 7.5.1.1
- -MAVC: See 7.4.3.2
- Ocular surface stains: See 7.4.3.4 and 7.4.3.5
- -Integral ophthalmological evaluation: Ver7.4.3.1
- -Evaluation of EA: See 7.4.3.1
- -ICO: See 7.4.3.2
- -Evaluation of the Subject's Diary: See 7.5.1.1
- Evaluation of adherence: See 7.5.1.1
- Return of PI and subject's diary: refers to the return by the subject, of the PI and the subject's diary to the research center.

#### 7.4.2 Unscheduled follow-up visits

At the request of the patient or any other individual related to the study, unscheduled follow-up visits may be carried out to report adverse events. During these visits, all pertinent data on reported adverse events should be collected and, where appropriate, an appropriate management plan should be established.

